5.7.1 Dose Modifications for chemotherapy

Because of the low weekly dosage of chemotherapy, we anticipate few dose modifications secondary to acute toxicities. Dose modifications are allowed and will be directed by the treating medical oncologist according to his/her discretion on an individual patient basis.

5.7.2 Changing Chemotherapy Regimens

In the event that cisplatin is held for 1 week and the patient is still deemed unable to receive further weekly cisplatin (because of cisplatin-related toxicity), patient will be switched to another protocol-acceptable weekly chemotherapy regimen (cetuximab, carboplatin/taxol, or carboplatin).

Other changes may be done on a case-by-case basis depending on the standard of practice of the treating medical oncologist.

5.8 Post-Chemoradiotherapy Assessment of Clinical Response

PET/CT will be performed 10 to 16 weeks (optimally at week 12) after CRT to assess response. All patients will be evaluated via clinical exam and fiberoptic laryngoscopy by the radiation oncologist and head and neck surgeon (optional) around the same time as the PET/CT scan. Note that the fiberoptic laryngoscopy need only be done once, at either 6 or 12 weeks post-CRT, with additional laryngoscopy procedures performed at the discretion of the physician. Decisions for surgical evaluation will be based on the results of the PET/CT and clinical exam at that time. Other optional imaging studies may be performed (e.g. CT scan 4 to 6 weeks after completion of CRT).

5.9 Surgery after CRT

Patients with a positive PET/CT scan will undergo surgical evaluation at the discretion of the surgeon. This may include biopsies and/or oncological resections of the primary tumor and lymph node metastases. The type of surgical procedure will be left to the discretion of the surgeon however the goal will be to remove any suspected residual tumor with a negative resection margin while maintaining organ preservation. Patients with a negative PET/CT scan will be observed.

5.10 Other Therapy

5.10.1 Permitted Supportive Therapy

All supportive therapy for optimal medical care will be given during the study period at the discretion of the attending physician(s) within the parameters of the protocol

5.10.1.1 Antiemetics

Prophylactic antiemetics and supportive therapy for nausea and vomiting are permitted and highly recommended in patients participating in this study. These interventions should be made according to institutional guidelines.

5.10.1.2 Nutritional Supplementation

Close monitoring of patients' volume status and body weight is strongly recommended. Nutritional supplementation through a nasogastric or gastrostomy feeding tube should be considered in patients who are unable to maintain hydration or experience more than 10% loss of body weight due to mucositis.

5.10.2 Non-permitted Supportive Therapy

5.10.2.1 Hematopoietic Growth Factors

Hematopoietic growth factors are not permitted during radiation therapy. Growth factors are only permitted if administered after radiation therapy has been completed. Erythropoiesis stimulating agents are not permitted.

5.10.3 Other Supportive Care Clinical Studies

Patients will be allowed to participate in other supportive care clinical studies that do not interfere with the treatment plan of the current study.

5.11 Duration of Study

The primary endpoint of this study is to evaluate the 2 year PFS rate after de-intensified CRT in HPV-positive and/or p16 positive OPSCC. Patient participation concludes after 2 years of follow-up after completion of CRT. However, patients will continue long-term routine follow-up as is our institutional policy.

5.12 Duration of Follow Up

After completion of treatment patients will be followed according to our institutional standard practice: clinical evaluations every 2 to 3 months for 2 years, every 6 months for 3 additional years, then yearly thereafter. As part of routine surveillance patients will receive chest imaging every 6 months for 2 years then yearly thereafter and thyroid function studies will be checked every 6 months for 2 years then yearly thereafter.

Our routine standard practice for all of our head and neck cancer patients is to encourage post-treatment dental follow-up and care. This study does not increase the need for post-treatment dental care or increase the risk of dental complication. In fact it may decrease the risk/incidence of post-treatment dental complications because the radiation dose is being reduced to 60 Gy. Thus we will continue to practice our routine post-treatment dental care recommendations.

See the Time and Events Table in the Appendix for a summary of the patient assessments/procedures and time periods.

6.0 ADVERSE EVENTS

6.1 Definition

An adverse experience is any untoward medical occurrence in a patient or clinical investigation subject administered a pharmaceutical product and which does not necessarily have a causal relationship with this treatment. An adverse experience or event (AE) can therefore be any unfavorable and unintended sign (including an abnormal laboratory finding), symptom, or disease temporally associated with the use of a medicinal (investigational) product, whether or not related to the medicinal (investigational) product.

Hospitalization for elective surgery or routine clinical procedures that are not the result of an AE (e.g., surgical insertion of central line) need not be considered AEs and should not be recorded as an AE. Disease progression should not be recorded as an AE, unless it is attributable by the investigator to the study therapy.

In this study, toxicity will be assessed according to the NCI Common Terminology Criteria for Adverse Events (CTCAE), version 4.0, available at:
http://ctep.cancer.gov/protocolDevelopment/electronic_applications/ctc.htm.

6.2 Reporting

Patients will be receiving radiation, chemotherapy, and surgical treatments within the accepted standard of care. We expect patients to experience the known toxicities that are associated with these standard treatments, but only at a lower rate and severity than patients treated with accepted radiation and chemotherapy dosing. Since treatments modalities are the same (radiation and chemotherapy), but doses of radiation and chemotherapy are reduced through this deintensification protocol, no adverse events will be attributable to the trial treatment. In the RTOG 0129 study, based on the same deintensification treatment, the overall rate of grade 3 or 4 acute toxic events was approximately 80% and the late grade 3 or 4 toxic events was approximately 25% of those seen in control patients treated with accepted radiation and chemotherapy doses. Because patients on this trial receive de-intensified chemotherapy and radiation by reducing the total dose of radiation to 60 Gy and administering no chemotherapy or Cisplatin 30mg/m² weekly the acute and late toxicities can only be decreased in trial patients compared to historical norms.

This de-escalation trial decreases radiation and chemotherapy doses compared to accepted dosing for head and neck cancer; therefore, adverse events will not be reported since there is no chance that adverse events are trial related.

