5.0 STUDY PLAN

5.1 Schema

[figure not shown]

Figure 2: Schema

Figure 2: The primary objective of this study is to assess the 2 year PFS of HPV-associated OPSCC after genetic risk based de-intensified CRT. All patients with ≤ 10 pack years smoking history will receive de-intensified CRT. Patients with > 10 pack years smoking history, and select patients with extensive smokeless tobacco history (based on the PI's assessment), will have genetic assessment of their tumors (pre-treatment archival tissue or biopsies), and if p53 is mutated, they will receive an additional 10 Gy for a total radiation dose of 70 Gy (which is the historical, standard) and one additional weekly chemotherapy dose. Those with > 10 pack year smoking history and without the p53 mutation will receive the de-intensified regimen. Circulating free HPV DNA will be assessed pre-treatment, during treatment, and post-treatment at months 3, 6, 12, 18, and 24 (See Section 5.5 for details on blood collection time points).

5.2 Pretreatment Evaluations: All patients will have standard of care evaluation and staging procedures.

5.2.1 Complete history and physical exam including weight and performance status.

5.2.2 Completion of panendoscopy with directed biopsies and bilateral tonsillectomies if the primary is unknown is strongly recommended, but not required.

5.2.3 Completion of the following radiological studies:

at least contrasted neck CT and chest x-ray. Chest CT, PET/CT and/or MRI are optional studies. CT of the neck should have IV contrast unless contraindicated (allergy or adverse reaction or renal issues). PET/CT is satisfactory and can be done instead of or in addition to contrasted neck CT and chest x-ray. Pretreatment ultrasound evaluation with possible FNA is permissible to stage the neck prior to treatment.

5.2.4 Complete dental evaluation is recommended.

5.2.5 Completion of the following laboratory studies: CBC, serum chemistries, liver function tests, and pregnancy test if female.

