5.6 Radiation Therapy

All patients will receive Intensity Modulated Radiotherapy Treatments (IMRT) or proton radiotherapy. All patients will be initially planned to 60 Gy at 2 Gy/fx, 30 fx, once a day. The turn around time for genetic testing of pre-treatment tissue (archival or biopsy) is approximately two weeks. It is expected that during the first couple of weeks fo the initial 60 Gy plan that the genetic analysis will be completed for the patients with > 10 pack years. Should one of these patients have a p53 mutation an additional 2nd radiation plan ("boost plan") of 10 Gy at 2 Gy/fx will be done. Thus the total dose for patients with HPV-associated OPSCC, > 10 pack years, and p53 mutated will be 70 Gy, the standard dose (two radiatons plans, sequential boost).

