Dose Specification: Dose painting IMRT, passive-scattered proton therapy, or intensity modulated proton radiotherapy (IMPT) will be used and all doses will be specified to the PTV. The PTV-HR and PTV-SR will be treated to the following respective total doses: 60 Gy and 50 Gy. The dose per fraction to the PTV-HR and PTV-SR will be 2 Gy per day and 1.67 Gy per day respectively for IMRT and IMPT. Because the passive scattered proton technique is not conducive to a dose-painting strategy, both the PTV-HR and PTV-SR will receive 2 Gy per day using a sequential boost. The total number of fractions will be 30. All fields will be treated once a day Monday through Friday. All patients will be initially planned to 60 Gy at 2 Gy/fx, 30 fx, once a day. The turn around time for genetic testing of pre-treatment tissue (archival or biopsy) is approximately two weeks. It is expected that during the first couple of weeks of the initial 60 Gy plan that the genetic analysis will be completed for the patients with > 10 pack years. Should one of these patients have a p53 mutation an additional 2nd radiation plan (“boost plan”) of 10 Gy at 2 Gy/fx will be made for the PTV-HR. Thus the total dose for patients with HPV-associated OPSCC, > 10 pack years, and p53 mutation will be 70 Gy (two radiaton plans, sequential boost).

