5.6.3 IMRT/Proton Treatment Planning

PTV's and PRV will be included in the radiotherapy optimization. Dose objectives will be chosen for the radiotherapy optimization based on previous institutional experience. Dose painting will be used to create one radiotherapy plan for IMRT and IMPT. The PTV-SR contours will encompass the PTV-HR contours. The dose to the PTV-SR plan will be 50 Gy at 1.67 Gy per daily fraction in 30 fractions. The PTV-HR will be treated to 60 Gy at 2 Gy per daily fraction in 30 fractions. For passive-scattered proton plans, a sequential boost technique will be allowed, and the dose to the PTV-SR will be 50 Gy at 2 Gy per daily fraction, and the PTV-HR will receive an additional 10 Gy (cumulative dose: 60 Gy) at 2 Gy per daily fraction. For those patients requiring a boost plan, the PTV-HR will receive an additional 10 Gy at 2 Gy per daily fraction in 10 fractions. IMRT/Proton radiotherapy to treat the entire neck is preferred, however a matched low anterior neck field photon technique may be used only if it does not result in significant dose heterogeneity for the PTV-HR. Proton therapy will be specified in Gy(RBE) (photon equivalents) to account for the inherent radiobiological differences between proton and photon therapies; thus, the treatments should be considered biologically equivalent.

5.6.4 Dose Constraints:

These apply to both patients who receive a total dose of 60 Gy or 70 Gy.

- PTV-HR and PTV-SR
 - 100% of the prescription should cover 95% of the PTV
 - No more than 1% of the PTV should receive $\geq 110\%$ of the prescribed dose

- No more than 1% of the PTV should receive $\leq 93\%$ of the prescribed dose
- Non-target Tissue
 - No more than 1% of the tissue outside the PTV should receive $\geq 110\%$ of the prescribed dose
- PRV
 - Spinal Cord: $0.1\text{cc} \leq 50\text{ Gy}$
 - Brainstem: $0.1\text{cc} \leq 54\text{ Gy}$
 - Parotid: Mean dose $< 26\text{ Gy}$ and/or $50\% < 30\text{ Gy}$
 - Cochlea: Mean dose $< 45\text{ Gy}$
 - Larynx: Mean dose $< 41\text{ Gy}$ and/or $60\text{ Gy} \text{ to } < 20\%$

PTV coverage should not be compromised to meet the dose constraints of the parotid, cochlea, or larynx. Sparing of these structures is left at the discretion of the treating radiation oncologists. The dose constraints for the spinal cord and brainstem must be satisfied. This may be done at the cost of altering the PTV.

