5.7 Chemotherapy

In our initial study, LCCC 1120, all patients were started on a regimen of cisplatin $30\text{mg}/\text{m}^2$ given intravenously over 60 minutes weekly during IMRT; 6 total doses for a total of $180\text{ mg}/\text{m}^2$. However, if cisplatin was not tolerated, it was permissible to switch to alternative, acceptable weekly chemotherapy regimens such as cetuximab, carboplatin, or carboplatin/taxol. For the proposed study, cisplatin is the preferred mandated first choice chemotherapy, however alternative weekly regimens are permissible. Typical reasons for a patient not being able to receive cisplatin include renal insufficiency and history of hearing loss. Justification for not using cisplatin must be documented.

Analysis of a prospective national registry, Longitudinal Oncology Registry of Head and Neck Carcinoma (LORHAN), showed that the three most commonly prescribed concurrent (with radiation) regimens (in order) are single agent cisplatin (51%), single-agent cetuximab (21%), and carboplatin plus paclitaxel (7%). Single agent carboplatin was infrequently used (3%) [redacted] et al. Cancer 2011;117:1679–86.). The acceptable weekly chemotherapy regimens that may be used on this study are the following:

- Cisplatin 30 to $40\text{ mg}/\text{m}^2$ (preferred, first choice)
- Cetuximab $250\text{mg}/\text{m}^2$ (preferred, second choice)
- Carboplatin AUC 1.5 and paclitaxel $45\text{ mg}/\text{m}^2$ (preferred, third choice)
- Carboplatin AUC 3 (preferred, fourth choice)

Chemotherapy will be given intravenously weekly during radiotherapy. 6 total doses will be given. It is preferred that the doses be administered on days 1, 8, 15, 22, 29, and 36;

however, this is not mandatory. Patients with the p53 mutation will receive one additional weekly chemotherapy dose. *Chemotherapy will not be given to patients with T0-2 N0-1 disease, < 10 pack years smoking history. For patients with T0-2 N0-1 disease, >10 pack years smoking history, whether or not the patient receives chemotherapy will be at the discretion of the treating physician.*

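### Section 6.2 waives adverse event reporting on a dose-reduction argument that is false for the 70 Gy group, and 5.6.3 prints that group's boost as 10 fractions where 5 are needed

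*Combined protocol and SAP*

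**What the plan says.** **Reporting.** Section 6.2 ends with the rule "therefore, adverse events will not be reported since there is no chance that adverse events are trial related". Its premise is that trial patients are de-intensified "by reducing the total dose of radiation to 60 Gy and administering no chemotherapy or Cisplatin" at 30 mg/m² weekly. It makes no exception for any group. It also states that no adverse event can be attributed to trial treatment and that toxicity can only fall relative to historical patients. As support it cites RTOG 0129 as a trial of the same de-intensified treatment, in which "the late grade 3 or 4 toxic events was approximately 25% of those seen in control patients treated with accepted radiation and chemotherapy doses".

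**Dose in the p53-mutated group.** Section 5.1 gives these patients "an additional 10 Gy for a total radiation dose of 70 Gy (which is the historical, standard) and one additional weekly chemotherapy dose". Section 5.6 agrees: "Thus the total dose for patients with HPV-associated OPSCC, > 10 pack years, and p53 mutated will be 70 Gy, the standard dose". The synopsis in 1.1 says that they are not de-intensified. Section 5.7 confirms the additional weekly dose. For T0-2 N0-1 disease with more than 10 pack years, however, "whether or not the patient receives chemotherapy will be at the discretion of the treating physician".

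**Boost.** Section 5.6.3 says: "For those patients requiring a boost plan, the PTV-HR will receive an additional 10 Gy at 2 Gy per daily fraction in 10 fractions".

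**Toxicity data.** Section 6.1 grades toxicity by CTCAE version 4.0 and defines an adverse event without requiring a causal link to treatment. The Time and Events Table (10.2) keeps a CTCAE row. Section 7.3 requires periodic reports to the DSMC.

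**The concern.** The rule in 6.2 decides what safety information is reported, and it rests on a stated fact about dose. The protocol defines two dose groups, and the fact is wrong for one of them. Patients at full standard radiation dose therefore lose adverse event reporting on an argument that does not describe their treatment. Toxicity is still graded under 6.1 and table 10.2, so the plan collects information that 6.2 says will not be reported.

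The boost line is a separate error affecting the same patients. It stands in the treatment-planning text, where a fraction count is an instruction. Its three numbers are mutually inconsistent, and following the count and the fraction size literally would exceed the intended total by 10 Gy.

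**Working it through.** **1. Initial plan (5.6).** Dose = fractions × dose per fraction = 30 × 2 = 60 Gy. This reproduces the stated figure.

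**2. Boost (5.6.3).** The inputs are 10 Gy, 2 Gy per fraction and 10 fractions.
- Keep the fraction size and count: 10 × 2 = 20 Gy; total 60 + 20 = 80 Gy in 30 + 10 = 40 fractions. The stated 10 Gy is not reproduced.
- Keep the dose and count: 10 / 10 = 1 Gy per fraction, against the stated 2 Gy.
- Keep the dose and fraction size: 10 / 2 = 5 fractions; total 70 Gy in 35 fractions.

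Only the third reading fits the rest of the protocol:
- Total dose: 5.1, 5.6, the Dose Specification paragraph and 5.6.4 all give 70 Gy for the higher-dose patients.
- Standard regimen: 1.2 gives 70 Gy in 35 fractions over 7 weeks.
- Weekly schedule: "All fields will be treated once a day Monday through Friday", so 35 fractions take 7 weeks and 40 take 8. One extra week matches one extra weekly chemotherapy dose.
- Passive-scattered proton plan (5.6.3): 50 Gy then 10 Gy, all at 2 Gy, is 25 + 5 = 30 fractions, the total stated under Dose Specification. There the same 10 Gy step takes five fractions.

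**3. The premise of 6.2 against the treatment sections.**
- Radiation: 6.2 assumes 60 Gy. The p53-mutated group receives 70 Gy, which is 10 Gy more and 0 Gy below the standard in 1.2.
- Number of chemotherapy doses, when given: 7 against 6; 7 / 6 = 1.17, or 17% more.
- Cisplatin dose: 6.2 names 30 mg/m². Section 5.7 allows 30 to 40 mg/m² and three other regimens, for all patients who receive chemotherapy.

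| Cumulative cisplatin | 30 mg/m² weekly | 40 mg/m² weekly |
|---|---|---|
| 6 doses | 180 | 240 |
| 7 doses | 210 | 280 |

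The standard in 1.2 is 2 to 3 × 100 = 200 to 300 mg/m²; in 1.3 it is 3 × 100 = 300. Seven doses lie inside the range of 1.2. Six doses at 40 mg/m² (240) also exceed the two-dose standard of 200. Lower chemotherapy exposure is thus assured against three standard doses but not against two.

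**4. The supporting citation.** Section 1.4 describes RTOG 0129 as a comparison of accelerated with standard fractionation, both with concurrent cisplatin. That is not the 60 Gy regimen of this trial. The sentence in 6.2 also leaves unclear whether its 80% and 25% are absolute rates or fractions of a control rate. The documents do not settle this.

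**5. Timing.** The waiver entered with Amendment 15 (18 August 2023). Section 7.1 ties the increases of 29 May 2019, 9 October 2019, 7 January 2020 and 17 June 2020 to accrual of 140, 160, 180 and 200 patients. Taking those dates as the accrual dates, 20 patients took 133, 90 and 162 days, or 54.9, 81.1 and 45.1 a year. At the fastest and slowest of these, the last 50 would enrol by 28 January to 27 July 2021. With up to 7 weeks of treatment, the last patient finishes by about mid-September 2021. Two years of follow-up then end between about March and September 2023. This is a projection; the documents do not say when enrolment closed.

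**The case against.** **Standard of care.** Section 6.2 opens by saying that treatment is within the accepted standard of care, and 70 Gy is exactly that. A ground for light reporting in this group therefore exists. This stands, but the no-reporting sentence is drawn from dose reduction, and standard-dose treatment gives no reason why toxicity could only be lower. Nor does presumed non-attribution take events outside 6.1, whose definition does not depend on causality.

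**Little left to report.** The amendment log shows that Amendment 8 (7 February 2019) had already limited adverse event reporting to 30 days after treatment, and Amendments 9 to 14 list no change to 6.2. On the projection above, the last 30-day window closed by about mid-October 2021, some 22 months before Amendment 15. A reader might infer that the waiver suppressed reports that were due. The documents do not support that: if the projection holds, none required by the previous rule remained. This stands, conditionally, and limits the practical effect.

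**An obvious misprint.** A reader might infer that patients were given 80 Gy. Nothing in the documents shows this. Four places give 70 Gy, including 5.6.4 directly after the error, and the dosing risk is low. It is still a wrong number in dosing text.

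**Safety oversight.** A reader might infer that the DSMC receives no toxicity data. Section 7.3 requires continuous monitoring and periodic formatted reports. The template is not in the documents, so that inference has no basis.

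**Conclusion.** Both places are wrong as written, and both are worth correcting at modest priority. The fraction count in 5.6.3 conflicts with its own dose and with the 70 Gy total; read literally it gives 10 Gy too much, and five fractions is the only consistent value. The reason for the waiver in 6.2 fails for the p53-mutated group, who receive 70 Gy and, when chemotherapy is given, 17% more weekly doses. It is also loosely stated for the 60 Gy group, because 5.7 permits higher cisplatin doses and other agents.

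The finding is not that p53-mutated patients are dosed above standard: 70 Gy is the standard. The number of patients at 70 Gy is not given and cannot be derived, and 1.6 suggests that such mutations are uncommon in this disease. The primary analysis, its critical values and its power are untouched. If enrolment closed in 2021, what remains to gain is mainly the later DSMC reports and a correct record.

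**What to change.** **5.6.3:** change the boost from 10 fractions to 5.

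**6.2:**
- Delete the no-reporting sentence, together with the statements that no adverse event is attributable to trial treatment and that toxicity can only be lower. Leaving either would contradict the new text.
- Insert, for example: *The radiation dose is reduced in the 60 Gy group only. Patients with a p53 mutation receive the standard 70 Gy and, if chemotherapy is given, one further weekly dose; the dose-reduction argument does not cover them. CTCAE grades collected under table 10.2 are summarised separately for 60 Gy and 70 Gy in the periodic DSMC reports (7.3).*
- Refer to 5.7 for the permitted chemotherapy instead of naming one regimen at one dose.
- Describe RTOG 0129 as a fractionation comparison, and say whether its 80% and 25% are absolute or relative to control.

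**Cost:** one number, a few sentences, and a two-column table in each remaining DSMC report. It needs no new visits, grading, committee or expedited-reporting duty. The table would be descriptive and would trigger no decision rule. The grading visits should be taken from the original Time and Events Table, because its columns are broken in the text available here.

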1.0 BACKGROUND AND RATIONALE

1.1 Study Synopsis

The proposed study is a follow-up study to LCCC 1120 and 1413. We have observed an excellent pathological complete response rate (LCCC 1120) and progression free survival (PFS) (LCCC 1413) in patients with HPV positive and/or p16 positive low-risk oropharyngeal squamous cell carcinoma (OPSCC) who received de-intensified chemoradiotherapy (CRT). We have shown that de-intensification is efficacious in these two phase II studies. We are leaders in the genomic classification of head and neck cancer, and investigators at LCCC ██████████ have shown that HPV-associated oropharyngeal cancer has a unique genetic profile. A major question is whether we can de-intensify in patients with HPV-associated oropharyngeal cancer who have smoking histories. The aim of the current study is to build upon our two phase II studies and the genomic profiling studies. Our hypothesis is that genomic profiling of patients' tumors (specifically for p53 mutations) will help in triaging patients to de-intensification versus standard of care. We will enroll patients with HPV-associated OPSCC regardless of smoking history and will assess p53 mutational status in patients with a smoking history. We will use the same de-intensification chemoradiotherapy regimen we have already evaluated in LCCC 1120 and 1413 in patients with HPV-associated OPSCC who have a minimal smoking history and in patients with a smoking history but with wild-type p53. If patients with a smoking history have mutated p53 they will not receive de-intensified chemoradiotherapy, but instead will receive standard doses. Our primary objective will be 2 year PFS. In LCCC 1413 the primary null hypothesis was 2 year PFS of 87%. We hypothesize, that by using genomics in the patients with a significant smoking history we will better select those who we can safely de-intensify and that the 2 year PFS will improve to 93%. We will also prospectively assess circulating free HPV DNA (cf-HPV-DNA) from blood samples. This study will be multi-institutional, with patients also enrolling at the University of Florida, Gainesville, Florida; the University of Florida Proton Therapy Institute, Jacksonville, FL; and Rex Cancer Center of Raleigh, Raleigh, North Carolina.

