1.4 Prospective Clinical Data on HPV positive HNSCC

Numerous retrospective studies have shown that patients with HPV-positive HNSCC have a significantly better prognosis than patients with HPV-negative HNSCC^{5,25,29}. These preliminary data have been verified in analyses of prospective clinical trials^{10,13,18}. Fakhry et al. evaluated the HPV status of 96 patients with laryngeal or oropharyngeal SCC from an Eastern Cooperative Oncology Group (ECOG) phase II trial. Patients with HPV positive tumors had higher response rates after induction chemotherapy (82% vs. 55%, p = 0.01) and CRT (84% vs. 57%, p = 0.007) as compared to those with HPV-negative tumors. The 2 year overall survival was also improved - 95% (HPV positive) vs. 62% (HPV negative). Lassen et al. analyzed the Danish Head and Neck Cancer Group (DAHANCA) 5 trial and observed an improved local-regional control, disease specific survival, and overall survival in patients whose tumors were p16 positive (a surrogate marker for HPV) versus those who were p16 negative¹⁸.

The RTOG 0129 prospective randomized trial also validated HPV positivity as being a strong, independent prognostic factor for overall and progression free survival¹⁰. RTOG 0129 compared accelerated fractionation radiotherapy with standard fractionation, both with concurrent cisplatin (2 cycles in the former and 3 cycles in the latter). There was no statistical difference in overall or progression free survival between the two arms. Post-hoc analysis of HPV status and outcomes in the OPSCC subset showed a significant improvement in OS (82.4%, vs. 57.1% at 3 year; P<0.001) and PFS in the HPV positive tumors. After accounting for other prognostic factors, HPV positivity conferred a 58% reduction in the risk of death (hazard ratio, 0.42; 95% CI, 0.27 to 0.66). Locoregional control was improved in the HPV-positive tumors; however, distant metastatic control and the rate of second malignancies were similar for both HPV-positive and negative OPSCC subgroups. Through recursive portioning analysis this OPSCC cohort was stratified into low, intermediate, and high risk groups for death (3 year OS of 93%, 70.8%, and 46.2% respectively). The factors used for stratification, in order of importance, were: HPV status, pack-years of tobacco smoking, tumor stage, and nodal stage. To be categorized as having low risk of death, a patient must have a HPV-positive

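### Section 6.2 waives adverse-event reporting on a ground that the protocol's own text does not support, and does not say which reporting is waived

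*Combined protocol and SAP*

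**What the plan says.** Section 6.2 (Reporting) first places the treatments within standard care and says "We expect patients to experience the known toxicities that are associated with these standard treatments, but only at a lower rate and severity". It then argues that, because doses are lower, no event can be attributed to the trial treatment and toxicity can only fall relative to historical experience. The regimen it has in mind is 60 Gy with "administering no chemotherapy or Cisplatin" at 30 mg/m² weekly. It cites a precedent: "In the RTOG 0129 study, based on the same deintensification treatment". It concludes that "adverse events will not be reported since there is no chance that adverse events are trial related".

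Other sections bear on this:

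- **Section 1.1**, on smokers with mutated p53: "they will not receive de-intensified chemoradiotherapy, but instead will receive standard doses".
- **Section 5.1**: "if p53 is mutated, they will receive an additional 10 Gy for a total radiation dose of 70 Gy", with one extra weekly chemotherapy dose. Section 5.6 likewise gives the total for patients with "p53 mutated will be 70 Gy, the standard dose".
- **Section 5.7** permits weekly cisplatin at 30 to 40 mg/m², cetuximab, carboplatin with paclitaxel, or carboplatin alone, for 6 doses.
- **Section 1.4**: "RTOG 0129 compared accelerated fractionation radiotherapy with standard fractionation, both with concurrent cisplatin".
- **Section 6.1** defines an adverse event regardless of cause and keeps CTCAE v4.0 grading; the Time and Events table (10.2) keeps a physician CTCAE row.
- **Section 7.3** keeps safety monitoring by the principal investigator and regular summaries to the DSMC.

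**The concern.** A safety rule is justified by a factual claim, and other parts of the same protocol disagree with that claim. The rule is also unqualified: it names no recipient, level of seriousness, time window or output. A reader cannot tell whether toxicity graded under Section 6.1 still reaches the DSMC or will appear in the final report. Followed literally, the sentence would let data that the protocol collects go unreported.

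This matters because lower toxicity is part of the case for de-intensification (Sections 1.3 and 1.5). The trial has no concurrent standard-dose arm, so the statement that toxicity can only fall is an assertion. The CTCAE data are the only trial material against which it could be examined.

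**Working it through.** No figure in the plan needs reproducing here. The check sets Section 6.2's premises beside the rest of the protocol.

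**1. Are doses reduced for everyone?** Standard radiation (Section 1.2) is 35 × 2 = 70 Gy.

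- p53 wild-type or minimal smoking history: 30 × 2 = 60 Gy; 60/70 = 85.7%, a 14.3% reduction.
- p53 mutated (Section 5.6): 60 + 10 = 70 Gy; 70/70 = 100%, a 0% reduction.

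The premise fails for the second group. The protocol does not give its size.

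**2. Is chemotherapy limited to none or cisplatin 30 mg/m²?** Section 5.7 says otherwise. Cumulative cisplatin is:

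- 6 doses: 6 × 30 = 180 to 6 × 40 = 240 mg/m²
- 7 doses (p53 mutated): 7 × 30 = 210 to 7 × 40 = 280 mg/m²
- Standard (Section 1.2): 2 × 100 = 200 to 3 × 100 = 300 mg/m²

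The ranges overlap, so a reduction does not hold for every patient against every version of the standard. Section 6.2 does not mention the non-cisplatin agents.

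**3. Is RTOG 0129 a precedent for the same regimen?** Section 1.4 describes a comparison of two fractionation schedules, each with cisplatin, and does not present it as this regimen. The two descriptions cannot both stand.

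**4. Does a lower rate mean no related events?** No. Section 6.2's own percentages (about 80% acute and 25% late grade 3–4) can be read as absolute or as relative to controls. For illustration with 250 patients:

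- Absolute: 0.80 × 250 = 200 acute; 0.25 × 250 = 62.5 late.
- Relative, late: 0.25 × 20% (Section 1.2) = 5%, or 12.5 patients.
- Relative, acute: Section 1.2 says only that most patients are affected. Assuming a control rate of 51% to 100%, 0.80 times that is 41% to 80%, or 102 to 200 patients.

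No reading gives zero. Elsewhere the protocol accepts treatment-related events: Section 5.7.2 changes regimen for cisplatin toxicity, Section 5.6.6 allows breaks for severe acute toxicity, and Section 6.1 foresees progression attributed to study therapy.

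**5. How many patients lose event reporting?** Only amendment decision dates are available (Section 7.1), not accrual dates. A month is taken as 30.44 days.

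- *Participation window (Section 5.11: 2 years after CRT).* Participation ends by 18 August 2023 if CRT ended by 18 August 2021. Allowing 6 to 7 weeks of CRT, the last enrolment must fall by 30 June to 7 July 2021, which is 12.4 to 12.6 months after 17 June 2020. The break-even pace for the last 50 patients is 50/12.4 to 50/12.6, about 4.0 a month.
- *Pace from 29 May 2019 to 17 June 2020:* (200 − 140) in 385 days (12.65 months) = 4.7 a month. Above break-even, so none remain in participation.
- *Pace from 7 January to 17 June 2020:* (200 − 180) in 162 days (5.32 months) = 3.8 a month. Below break-even, so about 3 remain (50 − 3.76 × 12.4 to 12.6).
- *30-day window.* The Amendment 8 summary limited reporting to 30 days after treatment. If that still applied just before Amendment 15 (assumption), only patients finishing CRT after about 19 July 2023 are affected. The break-even pace is then 50 over about 35.5 months = 1.4 a month, and zero becomes more likely.
- *Final report.* If the waiver reaches it, toxicity already collected on every patient is in question.

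The answer changes with the window and with the interval used for the pace, so no single count can be defended.

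**The case against.** The best defence is that assessing and reporting are different acts. Section 6.1 defines and grades events, while Section 6.2 concerns reporting. Section 7.3 does not say that its summaries consist of event reports, and it lets the DSMC and PRC ask for more. Section 8.5.3 still mentions an IRB route for unanticipated problems. The Amendment 15 summary speaks of trial-related event reporting and of removing site-specific language, which suggests that only individual reports were meant to stop. Standard-of-care treatment could also be a reason to limit individual reports of expected events.

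Much of this stands. A reader might infer that Section 6.2 flatly contradicts Sections 6.1, 7.3 and 10.2; the documents show tension, not contradiction, because the waiver's scope is unstated. The amendment summary makes the narrow reading more plausible but does not settle it, since the current sentence is unqualified.

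A reader might also infer that p53-mutated patients receive more than standard treatment. The extra dose is one more than the trial's 6, and 210 to 280 mg/m² of cisplatin lies within the protocol's standard 200 to 300. Nor do the wider options in Section 5.7 show higher toxicity; they show that Section 6.2's description is incomplete.

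What does not stand is the stated ground. Neither standard-of-care treatment nor a lower expected rate makes a related event impossible.

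**Conclusion.** The point holds as a wrong justification for a stated safety rule, together with an undefined scope. The premise of reduced dose fails outright for p53-mutated patients (0% radiation reduction), the regimen description is incomplete, the RTOG 0129 sentence conflicts with Section 1.4, and the expected toxicities are not zero.

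The number of patients affected cannot be derived. For individual event reports after 18 August 2023 it may be zero. A reader might take the last 50 of 250 (20%) as an upper limit, but that covers only patients possibly still in two-year participation and assumes that the final report is outside the waiver; if it is inside, all patients could be affected. The accrual paces rest on amendment dates and on the assumption that they continued.

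The PFS analysis is not affected. It should be fixed because the rule, followed as written, permits collected toxicity data to go unreported.

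**What to change.** Reconcile Section 6.2 with Sections 1.1, 1.4, 5.1, 5.6, 5.7, 6.1, 7.3 and 10.2. Specifically:

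- Delete the three absolute statements: that no event can be attributed to trial treatment, that toxicity can only fall, and that trial-relatedness is impossible.
- Correct or remove the RTOG 0129 sentence.
- State that the CTCAE v4.0 data already collected, including serious events, are summarised for the DSMC under Section 7.3 and in the final report. A split by assigned dose group would be useful but is optional.
- If any individual-event reporting is still to be waived, say which, and to whom it would otherwise have gone.

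The cost is tabulating assessments already planned, plus an amendment that needs IRB approval at UNC and, under Section 8.6, local approval at sites using their own IRB. No dose or clinical rule is proposed.
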